**Variables:**

Exposure: The exposure to the following will be considered:

1. Aspirin
2. Aspirin-clopidogrel combination\*
3. Clopidogrel\*
4. Warfarin
5. NOACs
  - Apixaban, Rivaroxaban, Dabigtran

\*[Note] Clopidogrel, Aspirin-clopidogrel will be included in descriptive analysis.

Outcome variables: The following outcomes will be assessed:

1. Effectiveness outcomes
  - Primary outcome: Composite of hemorrhagic stroke, ischemic stroke, and systemic embolism
  - Secondary outcomes: Individual outcome of hemorrhagic stroke, ischemic stroke, and systemic embolism
2. Safety outcomes

- Primary safety outcome: Major bleeding including gastrointestinal bleeding or intracranial bleeding and other bleeding
- Secondary safety outcomes: Individual outcome of major bleeding

**Key-Covariates:** Variables, including, but not limited to, will be age, sex, types of health insurance, CHA2DS2-VASc score, HAS-BLED score, Charlson Comorbidity Index score, etc.

**Data sources:** The Korean Health Insurance Review & Assessment Service (HIRA) database from January 1, 2007 to November 30, 2016 will be used for the analysis. The HIRA database contains the data of universal health insurance system in Korea. The database contains patients' demographic information, their use of inpatient and outpatient services, and pharmacy dispensing claims.

**Study size:** Based on HIRA disease statistics, the number of patients with atrial fibrillation (KCD code: I48) were 148,130 and 169,259 in 2015 and 2016, respectively. Thus, the anticipated number of patients will be approximately 150,000 since we plan to include patients who already had atrial fibrillation and were prescribed with aspirin, warfarin, or NOACs from July 1, 2015 to November 30, 2016. However, the study size might change after applying inclusion and exclusion criteria.

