2.1 STUDY DESIGN

This study will use a retrospective cohort design in which the treatment effectiveness and safety outcomes of new use of NOACs compared to other NOACs, new use of warfarin, and aspirin will be estimated in patients with atrial fibrillation using the Korean Health Insurance Review & Assessment Service (HIRA) database. Comparative analyses will be performed contingent on a feasibility assessment based on the descriptive analyses. Propensity score method and Cox proportional hazards models will be used to account for selection bias, differences in follow-up time, and right data censoring. This will allow us to minimize selection bias and confounding bias and provide outcome data amenable to rapid clinical interpretation (i.e., time-to-event analysis, hazard ratios). Furthermore, HIRA database will allow us to preserve the population-based longitudinal data collection advantages. The overall study design is described in Figure 1.

[figure not shown]

Figure 1. Study design scheme

Study population

Subjects with atrial fibrillation (between January 1, 2007 up to and including the index date*) who newly initiated NOACs, warfarin, or used aspirin between July 1, 2015 and November 30, 2016 in the Korean Health Insurance Review & Assessment Service (HIRA) database.

*Index date is the first prescription date of study drugs, including NOACs, warfarin, and aspirin.

Data source

South Korea has a universal health coverage system that the National Health Insurance covers approximately 97% of the overall South Korean population. The claims data of Health Insurance Review & Assessment Service (HIRA) contains 46 million patients per year that account for 90% of the total population in Korea and include claims from almost 80,000 healthcare service providers across South Korea as of 2011.

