6. For the comparison of “NOAC versus NOAC”, and “NOAC versus warfarin”, patients with any OACs (apixaban, dabigatran, rivaroxaban, or warfarin) in the pre-index period (from 1 year prior to the day before index date)
 - *[NOTE] Patients prescribed antiplatelets in the pre-index period will not be excluded.*
7. For the comparison of “NOAC versus aspirin”, patients with following medications in the pre-index period (from 1 year prior to the day before index date)
 - NOAC user: OACs (apixaban, dabigatran, rivaroxaban, warfarin)
 - Aspirin user: none
 - *[NOTE] NOAC user is defined as OAC naïve user and aspirin user is allowed to have OACs or antiplatelets in the pre-index period.*

Cohorts

To avoid increasing type I error when multiple comparisons occur, this full analysis set will be splitted into multiple sub-analysis sets as follows:

1. NOAC vs NOAC (both as OAC naïve users)
 - A. Sub-dataset 1: patients with index treatment of apixaban and patients with index treatment of dabigatran
 - B. Sub-dataset 2: patients with index treatment of apixaban and patients with index treatment of rivaroxaban
 - C. Sub-dataset 3: patients with index treatment of dabigatran and patients with index treatment of rivaroxaban

[NOTE] The index date will be defined as date of the first prescription of NOAC in patients with NVAF. To identify new users, a look-back observation period from 1 year prior to the day before the index date will be used and must indicate no OAC use during this period. The diagnosis date of NVAF could occur from January 1, 2007 up to and including the index date.

2. NOAC vs warfarin (both as OAC naïve users)
 - A. Sub-dataset 4: patients with index treatment of apixaban and patients with index treatment of warfarin
 - B. Sub-dataset 5: patients with index treatment of dabigatran and patients with index treatment of warfarin
 - C. Sub-dataset 6: patients with index treatment of rivaroxaban and patients with index treatment of warfarin

[NOTE] The index date will be defined as date of the first prescription of NOAC or warfarin in patients with NVAF. To identify new users, a look-back observation period from 1 year prior to the day before the index date will be used and must indicate no OAC use during this period. The diagnosis date of NVAF could occur from January 1, 2007 up to and including the index date.

3. NOAC (OAC naïve user) vs aspirin (no restrictions of antiplatelet or OAC use in the pre-index period)

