 - A. Sub-dataset 7: patients with index treatment of apixaban and patients with index treatment of aspirin
 - B. Sub-dataset 8: patients with index treatment of dabigatran and patients with index treatment of aspirin
 - C. Sub-dataset 9: patients with index treatment of rivaroxaban and patients with index treatment of aspirin

[NOTE] The index date will be defined as date of the first prescription of NOAC or aspirin in patients with NVAF during the intake period (from July 1, 2015 to November 30, 2016). To identify NOAC users, a look-back observation period from 1 year prior to the day before the index date will be used and must indicate no OAC use during this period. However, OAC use or antiplatelet use during a look-back observation period from 1 year prior to the day before the index date will be allowed for aspirin users. The diagnosis date of NVAF could occur from January 1, 2007 up to and including the index date.

Each patient was followed until discontinuation or switching of index treatment, outcome occurrence, or study ends (November 30, 2016).

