5 STATISTICAL METHODOLOGY AND STATISTICAL ANALYSES

5.1 STATISTICAL METHODS

Descriptive Analysis:

- All outcome variables will be summarized descriptively through the tabular and graphical display of mean values, medians, ranges, and standard deviations for continuous variables of interest and frequency distributions for categorical variables.
- The proportion of antithrombotics (aspirin, clopidogrel, aspirin and clopidogrel combination, warfarin, NOACs) at index date will be examined.
- Appropriate tests (e.g., t-test, chi-square test) will be used based on the distribution of the measure. The $p < 0.05$ considered significant.

Multivariate Analysis:

Propensity score method

The estimation of propensity score will be performed to control for confounders in each sub-dataset: (1) each NOAC versus NOAC; (2) each NOAC versus warfarin; (3) each NOAC versus aspirin.

Propensity scores are estimated by logistic regression analyses that incorporate potential treatment predictors as independent variables and types of index treatment as dependent variable (e.g., apixaban=1, warfarin=0). Covariates in the logistic regression model will

include variables such as age, sex, CCI score, CHA₂DS₂-VASc score, HAS-BLED score, and comorbidities, but the final list of these covariates will be discussed and determined after reviewing the results of descriptive analysis of the pre-matched datasets. Further, we will report the *c*-statistic of the propensity score that indicates the degree to which the propensity score model discriminates between treated patients and untreated patients.

After estimation of propensity score, we will perform propensity score matching (PSM). 1:1 matching without replacement will be performed.

The populations would be first matched using PSM according to their index treatment. For these matched populations we should then explore the proposed subgroups by: making an assessment of patient numbers in the subgroups and checking that patient characteristics are still similar between the index treatments in the subgroups. If they are similar, then conduct interaction term analysis is being conducted to determine whether the treatment effect varies between the subgroups. If the populations are no longer similar in characteristics, then re-matching via PSM will be performed for the subgroups.

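### Sub-datasets 7-9 have no rule for anticoagulants taken on the index date, so anticoagulated patients can enter the aspirin arm and same-day NOAC-plus-aspirin patients fit both arms of their NOAC's comparison

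*SAP*

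**What the plan says.** SAP 3.1 (Cohorts) splits the full analysis set into nine pairwise sub-datasets, each defined only by index treatment. Two examples are "Sub-dataset 4: patients with index treatment of apixaban and patients with index treatment of warfarin" and "Sub-dataset 7: patients with index treatment of apixaban and patients with index treatment of aspirin". For 7-9 the note reads: "The index date will be defined as date of the first prescription of NOAC or aspirin in patients with NVAF during the intake period". Warfarin does not appear in that definition.

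SAP 2.1 has a wider one: "Index date is the first prescription date of study drugs, including NOACs, warfarin, and aspirin". The population statement in the Protocol abstract agrees with it. Neither definition says what happens when two study drugs are prescribed on the same day.

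Exclusions 6 and 7 (Protocol 8.2.2, SAP 3.1) cover the year ending the day before the index date. For the aspirin comparison, NOAC users must be OAC-naive, whereas "aspirin user is allowed to have OACs or antiplatelets in the pre-index period".

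SAP 5.1 fits a logistic propensity model with "types of index treatment as dependent variable (e.g., apixaban=1, warfarin=0"). It adds a sensitivity analysis based on a multinomial propensity score.

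The only drug combination the plan names is aspirin with clopidogrel. The Protocol abstract lists it as a separate exposure and notes: "Clopidogrel, Aspirin-clopidogrel will be included in descriptive analysis".

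**The concern.** Arm membership depends on what is prescribed on the index date, but no rule looks at that date for a second drug or for OAC supply still running. This leaves two gaps.

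- **Anticoagulated patients in the aspirin arm.** Because warfarin is not an index drug in 7-9 and aspirin users have no OAC restriction, someone taking aspirin on top of an anticoagulant qualifies as an aspirin patient.
- **Overlapping arms.** A patient given a NOAC and aspirin on the same day meets both arm definitions for that NOAC, and the propensity model cannot take such a patient without a further decision.

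NOAC versus aspirin serves primary objectives 2 and 3. If part of the aspirin arm is anticoagulated, the contrast is no longer between a NOAC and aspirin. Two programmers following the SAP faithfully could also build different cohorts.

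**Working it through.** **1. Plan's own figure.** There is none to reproduce. The documents give no count of index-day combinations and no share of aspirin users with OAC supply in hand.

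**2. The arm definitions applied literally**, for patients with no OAC in the previous year:

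| Drugs on index date | Sub-datasets 1-3 | Sub-datasets 4-6 | Sub-dataset 7 | Sub-datasets 8 and 9 |
|---|---|---|---|---|
| Apixaban | apixaban arm of 1, 2 | apixaban arm of 4 | apixaban | none |
| Aspirin | none | none | aspirin | aspirin |
| Apixaban + aspirin | apixaban arm of 1, 2 | apixaban arm of 4 | **both arms** | **aspirin** |
| Warfarin + aspirin | none | warfarin arm of 4, 5, 6 | **aspirin** | **aspirin** |

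Dabigatran and rivaroxaban behave the same way in 8 and 9. Under the wider SAP 2.1 definition, warfarin + aspirin is instead a tie that nothing resolves.

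For patients with earlier OAC use, aspirin prescribed while OAC supply is running places them in the aspirin arm. A NOAC and aspirin on the same day fails the NOAC arm's naive-user rule but still satisfies the aspirin arm.

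**3. Does a later rule remove this person-time?**

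- SAP Table 3 defines switching among anticoagulants as a non-index OAC filled within 30 days after discontinuation. A patient who continues both drugs never discontinues, so the rule is not triggered.
- Protocol 8.3 ends follow-up at a switch to another study drug, but does not say how drugs started together, or an OAC already in use, are treated.
- The baseline medications in SAP Tables 4 and 12 do not include OACs. The covariate list is open, but adjustment cannot decide which arm a dual-qualifying patient belongs to.

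**4. Illustration: OAC users in the aspirin arm.** All inputs are assumptions and the ratios are crude. Let d be the share of aspirin-arm person-time on OAC plus aspirin.

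Bleeding, with a true ratio of 1.00 and OAC plus aspirin at b times the aspirin-alone rate: observed ratio = 1 / [(1 - d) + d x b].

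- d = 5%: 1/1.025 = 0.976 (b = 1.5); 1/1.05 = 0.952 (b = 2.0)
- d = 10%: 1/1.05 = 0.952; 1/1.10 = 0.909
- d = 30%: 1/1.15 = 0.870; 1/1.30 = 0.769

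Stroke, with a true ratio of 0.50 and OAC plus aspirin at r times the aspirin-alone rate: observed ratio = 0.50 / [(1 - d) + d x r].

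- d = 5%: 0.50/0.97 = 0.515 (r = 0.4); 0.50/0.98 = 0.510 (r = 0.6)
- d = 10%: 0.50/0.94 = 0.532; 0.50/0.96 = 0.521
- d = 30%: 0.50/0.82 = 0.610; 0.50/0.88 = 0.568

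The primary composite includes hemorrhagic stroke, so r must be read as a net ratio over all components.

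**5. Illustration: same-day NOAC + aspirin patients.** Let g be their share of the arm or arms that receive them.

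- *All placed in the NOAC arm* (true bleeding ratio 1.00, rate 1.5-2.0 times): ratio = (1 - g) + g x b. This gives 1.05-1.10 at g = 10% and 1.15-1.30 at g = 30%, so the NOAC looks worse.
- *All placed in the aspirin arm*: the step 4 bleeding formula applies and the ratio falls.
- *Counted in both arms* (true ratio 0.70, rate 1.5 times aspirin alone): ratio = [(1 - g) x 0.70 + g x 1.5] / [(1 - g) + g x 1.5]. At g = 5% this is 0.740/1.025 = 0.722; at g = 30% it is 0.940/1.150 = 0.817. The ratio moves toward 1.

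**The case against.** Four points on the other side carry weight.

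- **The plan handles one combination.** Aspirin with clopidogrel is a separate exposure in the Protocol abstract and a separate index-date category in SAP 5.1. The natural reading is that such patients are not aspirin patients in 7-9. A reader might infer that no combination is covered at all; the documents do not support that. At most, a sentence confirming the exclusion is missing.
- **The overlap is limited.** A reader might conclude that a same-day NOAC-plus-aspirin patient sits in both arms of all three aspirin comparisons. It is both arms of one and the aspirin arm of the other two.
- **The bias is not all in one direction.** A reader might infer that the gap always makes the NOAC look safer. That tendency applies to anticoagulated patients in the aspirin arm. For same-day NOAC-plus-aspirin patients, step 5 shows movement down, up or toward 1, depending on placement.
- **Earlier OAC use among aspirin users is allowed on purpose**, and nowhere does the plan say that the aspirin arm represents patients free of anticoagulation. This stands as far as past use goes. The allowance concerns the pre-index period, however, and does not address treatment running on the index date.

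There is also partial mitigation: comparative analyses depend on the descriptive results, and SAP 5.1 tabulates antithrombotics at index first. That list has no OAC-plus-aspirin category, so it would not bring these patients to light.

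**Conclusion.** The gap is real and should be closed before the cohorts are programmed. As written, the rules for 7-9 admit anticoagulated patients to the aspirin arm and create overlapping arms under models that need one treatment per patient. This is more than missing detail, because following the text exactly produces the problem.

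The size is unknown. If OAC plus aspirin carries 1.5-2.0 times the bleeding rate of aspirin alone, a true bleeding ratio of 1.00 would appear as 0.95-0.98 with 5% contamination and 0.77-0.87 with 30%. The effect is therefore minor or material depending on a proportion the documents do not give. The shift of the stroke ratio toward 1 further assumes that the NOAC truly lowers the composite and that OAC plus aspirin has a lower net rate of it than aspirin alone.

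**What to change.** In SAP 3.1 and Protocol 8.2.2:

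- For 7-9, state that the aspirin arm requires no OAC prescription (warfarin included) and no OAC days' supply on the index date. Past OAC use that has ended stays allowed.
- Leave same-day NOAC-plus-aspirin patients out of 7-9 and report their number in the patient flow.
- Leave patients with two different OACs on the index date out of 1-6. State that antiplatelet use on the index date is allowed equally in both arms of 1-6, because the present note covers only the pre-index period.
- Use the same single-treatment assignment in the multinomial propensity model.
- If aspirin with clopidogrel stays out of the aspirin arm, as the Protocol abstract and SAP 5.1 imply, apply the same clopidogrel rule to the NOAC arm of 7-9.

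The cost is a short set of cohort rules, added flow counts and smaller arms in 7-9. How much smaller cannot be judged from the documents and should be reported.

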3.2 SUBGROUPS

Subgroup analysis may be considered, including but not limited to subgroup analyses by CHA₂DS₂-VASc score, HAS-BLED score and the dose of index treatment.

4 ENDPOINTS AND COVARIATES

4.1 EFFICACY/ EFFECTIVENESS ENDPOINT(S)

Table 1. Effectiveness Endpoints

Variable	Role	Operational definition
Stroke/Systemic embolism	Primary effectiveness outcome	Hemorrhagic stroke, ischemic stroke and systemic embolism requiring hospitalization will be identified using hospital claims which had a hemorrhagic stroke, ischemic stroke or systemic embolism code whichever came first (i.e., the first occurred event will be used). All KCD diagnosis codes (main and sub-diagnosis codes) will be used. Especially, hospitalization and brain CT or MRI codes will be needed to identify ischemic stroke and hemorrhagic stroke. For systemic embolism, hospitalization and any CT or MRI codes will be used (Appendix 2, Table 7).
Individual outcome of primary outcome	Secondary effectiveness outcome	Individual outcome of hemorrhagic stroke (diagnosis codes in all main and sub-diagnosis codes + hospitalization + brain CT or MRI), ischemic stroke (diagnosis codes in all main and sub-diagnosis codes + hospitalization + brain CT or MRI), and systemic embolism (diagnosis codes

Variable	Role	Operational definition
		in all main and sub-diagnosis codes + hospitalization + any CT or MRI)

4.2 SAFETY ENDPOINTS

Table 2. Safety Endpoints

Variable	Role	Operational definition
Major bleeding	Primary safety outcome	Bleeding requiring hospitalization will be identified using hospital claims which had a bleeding diagnosis code as the first occurred KCD code and it will be consisted of intracranial hemorrhage (ICH) and gastrointestinal (GI) bleeding, and other bleeding (Appendix 2, Table 8). All KCD diagnosis codes (main and sub-diagnosis codes) will be used. Especially, hospitalization and brain CT or MRI codes will be needed to identify ICH.
Individual outcome of major bleeding	Secondary safety outcome	Individual outcome of ICH (diagnosis codes in all main and sub-diagnosis codes + hospitalization + brain CT or MRI), gastrointestinal bleeding (diagnosis codes in all main and sub-diagnosis codes + hospitalization), and other bleeding (diagnosis codes in all main and sub-diagnosis codes + hospitalization)

4.3 OTHER ENDPOINTS

Table 3. Other Endpoints

Variable	Role	Operational definition
Discontinuation	Outcome	Discontinuation is defined as the first day of a period of at least 30 consecutive days after the calculated time to finishing the pack based on pack size and number of tablets per day. The date of discontinuation will be the end date of the last filled prescription before the treatment gap.
Switching	Outcome	A switch among anticoagulants will be defined as a prescription filled for non-index OAC within 30

Variable	Role	Operational definition
		days after the date of discontinuation.
Clinical events preceding each pattern	Outcome	
Types of event* preceding each pattern (i.e., discontinuation, switching)
 
[*Note] Events will include but not limited to (1) serious clinical events where physicians might consider changing anticoagulants (e.g., thromboembolic events (e.g., stroke/systemic embolism, venous thromboembolism [codes in Table 7]), major bleeding [codes in Table 8]); (2) the occurrence of a contraindication for OACs (e.g., valvular atrial fibrillation, severe kidney disease); and (3) procedure for atrial fibrillation that might not require OACs (e.g., elective defibrillation, radiofrequency ablation, and left atrial appendage occlusion [codes in Table 13]).

Compliance (medication possession ratio, MPR)	Outcome	
Medication possession ratio (MPR) will be calculated as total days of index treatment dispensed / 365 days of study follow-up.
 
Patients with an MPR greater than 1 will be capped at 1.

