Exclusion criteria	Exclusion criteria	HIRA database	
Claims with the following KCD codes or procedure codes:
 
 
1. Valvular AF/ Prosthetic heart valves: I05, I08, I09, I34, Q23, T820, T826, Z952, Z953, Z954            - Korean procedure codes: M6580, M6581, M6582, O1791, O1792, O1793, O1794, O1795, O1796, O1797, O1798, O1799, M6531, M6532, M6533, O1690, O1730, 1740, O1750, O1760, O1770, O1781, O1782, O1783, O1810, O1826
 
2. End-stage of chronic kidney disease/dialysis: N185, T824, Y602, Y612, Y622, Y841, Z49, Z992, E1022, E1122, E1222, E1322, E1422
 
3. Kidney transplant: Z940
 
4. Venous thromboembolism: I636, I676, I801, I802, I803, I808, I809, I81, I822, I823, I829, I26
 
5. Hip or knee replacement            - Korean procedure codes: N0711, N0715, N1711, N1715, N1721, N1725, N2070, N2072, N2077, N2710, N2712, N2717, N3710, N3712, N3717, N3720, N3722, N3727, N4710, N4712, N4717, N4720, N4722, N4727
 
6. Thyrotoxicosis: E05
 
7. Pericarditis: I30, I31, I32
 
8. Hypertrophic cardiomyopathy: I422
 
9. Elective defibrillation, radiofrequency ablation, or left atrial appendage occlusion            - Korean procedure codes: M5880, M6540, M6542, M6545, M6547, M6511
 

Follow-up period	Follow-up period	HIRA database	
From the index date until the first occurrence of the following whichever came first:
 
 
1. Discontinuation: maximum of a 30-day gap after the calculated time to finishing the pack based on pack size and number of tablets per day. Switching: switch to any other study drugs
 
2. Outcome occurrence
 
3. Study ends: November 30, 2016
 

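### As most naturally read, the plan counts a stroke or bleed in a supply gap only if a refill follows within 30 days, which can bias rates and hazard ratios

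*SAP*

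**What the plan says.** SAP 4.3, Table 3 defines discontinuation as one of the drug-use outcomes: "Discontinuation is defined as the first day of a period of at least 30 consecutive days after the calculated time to finishing the pack". The next sentence fixes its date: "The date of discontinuation will be the end date of the last filled prescription before the treatment gap".

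SAP 3.1, under Cohorts, uses the same term to end outcome follow-up and gives no separate censoring date: "Each patient was followed until discontinuation or switching of index treatment, outcome occurrence, or study ends (November 30, 2016".

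The follow-up row of Protocol 8.3 runs "From the index date until the first occurrence of the following whichever came first". The first reason listed is "Discontinuation: maximum of a 30-day gap after the calculated time to finishing the pack". The row does not say whether follow-up then ends on the last supplied day or when the gap has run out. It also lists "Switching: switch to any other study drugs", whereas SAP Table 3 limits a switch to a non-index OAC filled within 30 days after the discontinuation date.

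SAP Table 3 names stroke, systemic embolism and major bleeding as examples of "serious clinical events where physicians might consider changing anticoagulants". The only analysis under the sensitivity heading of SAP 5.1 is weighting by a multinomial propensity score. Nothing tests the gap length or the censoring date.

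**The concern.** Follow-up time should be classified from what is known up to that time. Here a gap day is accepted or rejected by looking ahead to see whether a refill arrives. That would be harmless if refilling had nothing to do with the outcome. But the outcomes are hospitalised strokes, emboli and bleeds, and the SAP itself expects such events to prompt treatment changes. Protocol 8.9.5 adds that reasons for stopping are not recorded, so event-driven stops cannot be picked out. Protocol 8.9.3 says mortality data are incomplete, so a patient who dies after an event in a gap simply never refills and is handled as discontinued.

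At stake are the primary effectiveness and safety comparisons. Propensity methods use baseline covariates and cannot repair censoring that depends on behaviour after the event.

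**Working it through.** **What the rule does.** Take supply ending on day 0 and a stroke on day 10.
- Refill on day 20: the gap is under 30 days, so there is no discontinuation. The stroke counts.
- No refill by day 30: discontinuation is dated day 0. The stroke falls after follow-up has ended and is not counted.
- No stroke, refill on day 20: all 20 gap days stay in the denominator.

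**Size.** The documents give no days' supply, gap lengths or refill rates, so there is no figure of theirs to reproduce and every input below is an assumption. Per dispensing cycle, with a rare event and a constant hazard:
- S = days supplied; q = share refilling within 30 days; G = mean gap in days among refillers
- k = chance that a would-be refiller still refills in time after an event in the gap
- m = chance that a would-be stopper refills in time after such an event

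Observed events are proportional to S + kqG + 30m(1−q), and observed person-time is S + qG. So

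observed rate / true rate = [S + kqG + 30m(1−q)] / [S + qG].

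With q = 0.90:

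| S | G | k | m | Calculation | Observed/true |
|---|---|---|---|---|---|
| 30 | 5 | 1 | 0 | 34.5/34.5 | 1.000 |
| 30 | 5 | 0.7 | 0 | 33.15/34.5 | 0.961 |
| 30 | 5 | 0.3 | 0 | 31.35/34.5 | 0.909 |
| 60 | 5 | 0.3 | 0 | 61.35/64.5 | 0.951 |
| 90 | 5 | 0.3 | 0 | 91.35/94.5 | 0.967 |
| 90 | 2 | 0.3 | 0 | 90.54/91.8 | 0.986 |
| 30 | 10 | 0.3 | 0 | 32.7/39 | 0.838 |
| 30 | 10 | 0 | 0 | 30/39 | 0.769 |
| 30 | 5 | 1 | 0.5 | 36/34.5 | 1.043 |

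In the first row 3.0 of 37.5 event-units up to supply end plus 30 days are dropped (8.0%), yet the rate is unbiased because the matching person-time goes too. In the third row the loss is 6.15 of 37.5 (16.4%), and the rate is low because would-be refillers' gap time stays in the denominator.

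With q = 0.92, S = 30 and k = m = 0, mean gaps of 2 and 7.2 days give 30/31.84 = 0.942 and 30/36.62 = 0.819. A simulation of nearly the same set-up (8% stopping at each refill, exponential gaps with means of 2 and 8 days truncated at 29 days) gave 0.929 and 0.815.

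**Apparent hazard ratio when the true one is 1** (ratio of two rows, q = 0.90):
- same S, G and k in both drugs: 1.00
- S = 30 versus 60 (G = 5, k = 0.3): 0.909/0.951 = 0.955
- S = 30 versus 90 (G = 5, k = 0.3): 0.940
- k = 0.3 versus 0.7 (S = 30, G = 5): 0.946
- S = 30, G = 10 versus S = 90, G = 2 (k = 0.3): 0.850
- S = 30, G = 10, k = 0 versus S = 90, G = 2, k = 0.3: 0.780

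**With gap time treated alike.** If everyone is followed to a refill or to supply end plus 30 days, events and person-time are both proportional to S + qG + 30(1−q). The ratio is 1.000 in every row, provided the hazard is the same on gap days as on supplied days.

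**A consequence that needs no refill assumption.** SAP Table 3 also plans to describe clinical events that precede discontinuation. An event in the gap that leads to stopping is dated after the backdated discontinuation, so it cannot be recorded as preceding it.

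**The case against.** The backdating sentence sits in a table of other endpoints, where discontinuation is itself an outcome serving the drug-utilisation objective. It is not labelled as the censoring rule. The row that is labelled as follow-up, in Protocol 8.3, does not backdate and could be read as ending when the 30-day gap has run. This stands as a reason not to treat the SAP reading as the only one. It does not remove the problem: SAP 3.1 uses the same word with no other date, and two programmers could build different primary analyses.

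A reader might infer that events are deleted unevenly between drugs, so that a drug with irregular refills looks safer and more effective. The documents do not support that. They give no refill behaviour by drug, dropped events take person-time with them, and an event during a lapse may prompt a restart, which pushes the rate up (1.043 above). The SAP says only that a change of anticoagulant might be considered, not that refilling stops. No refilling at all after an event is a corner case, since the data also cover inpatient care and the SAP does not say whether drug given in hospital counts as supply. Uncaptured over-the-counter supply (Protocol 8.9.5) makes different measured gaps plausible for aspirin, but does not establish them.

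Ending follow-up at supply end also has a proper purpose: it limits untreated time counted as treated. That stands, and is why it should remain as a sensitivity analysis. Finally, under the Protocol's separate switching entry, a gap event followed by a switch might still count. That depends on which switching definition governs, and again calls for reconciliation.

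**Conclusion.** The concern holds in a conditional form. On the natural reading, whether a gap event counts depends on a refill made within 30 days of supply end and after the event, and no planned analysis tests this. Rates are biased if an event changes the chance of refilling, which the SAP's own text makes plausible. Hazard ratios are biased if, in addition, supply length, gap length or the response to an event differs by drug, which the documents leave open.

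Size and direction are unknown. Under the assumed inputs the observed rate is about 0.82 to 1.04 of the true rate, with 0.77 at the most extreme and exactly 1 when events do not affect refilling. The null hazard ratio ranges from 1.00 with shared parameters to 0.78 in the most extreme contrast tried; reversing the comparison inverts these ratios. What is firm is that the documents do not fix one end-of-follow-up date and that the SAP's date uses future information.

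**What to change.** In both documents, state one end of follow-up for the outcome analyses that does not depend on fills made after an event. Count events and person-time up to supply end plus 30 days for every patient, unless a refill extends supply or a switch, an outcome or the study end comes first. Align SAP 3.1, SAP Table 3 and the follow-up row of Protocol 8.3 to this, and use one switching definition, since switching also ends follow-up. Keep censoring at supply end as a sensitivity analysis, and say there how patients are handled whose supply ends fewer than 30 days before November 30, 2016, because their gap cannot be fully observed. For the descriptive objective, say how an event inside the gap is placed relative to discontinuation.

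Confirm too that event dates are available to the day. Protocol 8.4 describes medical claims as stamped by month and year; if that is literal, the order of supply end and event may not be recoverable.

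The cost is a wording change and a small programming change. The downside is that up to 30 days of possibly untreated time is attributed to the index drug, and the hazard may differ on those days. The supply-end sensitivity analysis shows how much the choice matters.
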